7.3 PARTICIPANT TESTING

Baseline and end assessments will be conducted in a single session for all participants. Sessions will last approximately 30-60 min., and will be conducted at Bournemouth University where possible, or in the participant's home via Zoom. 'At-home' test sessions will be used if participants are unable or unwilling to come to the University, and are intended primarily to allow the trial to continue during the COVID-19 pandemic when National lockdown measures and precautions were recommended in the UK (March 2020 - July 2021). These home test sessions may also open the trial to participants who would otherwise be unable to take part, primarily due to location, enhancing study inclusivity. Participants will be tested in the same location at both baseline and trial end, as possible.

All participants will complete the same measures regardless of their completion of test sessions at the University or 'at-home', with a few exceptions: Participants who are tested 'at-home' will not undertake the sweet taste perception and preference tests, the sweet food choice test, nor the solution-based measures of sweet liker status. Participants who are tested 'at-home' will also complete their own anthropometric measurements, but they will do this while the trial researcher observes via Zoom. Comparability across all measurements will be facilitated by involvement of the same researcher both at the University or 'at-home'.

All sessions will commence before 11am to allow individuals to undertake the measures in a fasted state, and will begin at the same time at baseline and trial end. The day before testing participants will also be asked to consume no alcohol, to consume nothing after 10pm, and to undertake no heavy exercise. Measures will be undertaken in the same order during each test session, as follows, or simply omitted: anthropometry; saliva sample; sweet liker status; PROP taste test; sweet taste test; and sweet food choice test. All questionnaires will be completed and checked for completion before the test session.

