This updated data from CSV2 was copied into a new file named CSV4. In CSV4 a helper column combining the participants ID number and log day (eg: JS19900.1, combination of JS1990 and 0.1) was used in combination with a new sheet to summarise all nutrients for each participant and each diet diary day. This resulted in 5120 unique daily totals across all nutrients. The CSV4 file was then saved as complete. Including all participants and screened non-participants a total of 70747 individual diary entries on the study via Nutritics Libro. Of these data, 67546 were participant entries and 3201 from non-participant screening diaries, with a total of 10757 unique food items logged.

Sweetener and sweet food counts

Foods that contained sweeteners, were high, medium or low in sugar were separated into counts for each diet diary. These counts were then added into 5 separate scores for the summation of foods consumed in each category for baseline, timepoints 1-4 and endpoint.

ALL DATA - MULTIPLE IMPUTATION

Main analyses were completed on an intention to treat basis as the gold standard for representing the applicability of the intervention in a real world setting rather than an ideal outcome. A variety of techniques to replace/analyse RCT results with missing data have been previously utilised including complete case analysis (CCA), single imputation (SI)(by last observation carried forward, mean or regression), multiple imputation or mixed-effect models (Bell et al., 2014; Li & Stuart, 2019; Ren et al., 2022). CCA and SI methods were discounted due to CCA not being reflective of real-world data, reducing statistical power and SI lacking uncertainty and most likely underestimating variance.

Instructions for the steps used to complete MI and the imputation sequence are included below. As multiple imputation is completed in the order of the variables within the analysis, the variables list was set as randomisation variables first, then nutrient values, anthropometrics and finally questionnaire data in the order that they were completed. All baseline variables were used as predictors, all endpoint variables used as imputations only due to the monotonic pattern.

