Where SPSS did not automatically pool results, Rubin's Rules for combining single estimates were used. The same multiple imputation guidelines were used for the basis for the imputation of all missing data. Where variables presented as having missing data, they were set as 'impute only' to ensure all predictor variables were not based on imputed data. The only difference was in one baseline waist circumference value that was missing in the original data and used in the 2nd MI predictors of the subsequent variables. This study took the premise of not generating imputations based on imputed data values. The same multiple imputation model was run for the initial analyses, adherence and variables completed by only lab participants. Multiple imputation for the adherence data used the same methods and predictors as for the main data set. The step by step methods used are included below. Adherence data points of each free sugar intake at each dietary data point were not included as predictors due to the fact that at least 1 time point needed to be imputed at each variable time point.

Instructions for multiple imputation in SPSS

1. Go to transform – random number generator. Select and set the active generator initialization at a fixed value of 950.
 - a. (This step is to provide a starting point/seed for the MI to enable results to be reproduced)
2. Then Analyze – multiple imputation – impute missing data values.
 - a. Variables tab
 - i. Input all variables for the model in the order they are to be used (this can be found in the output document and also to summarise at the end of this doc) but is all endpoint and corresponding baseline variables, therefore excluding demographics. But including gender. (The order is central for reproducing)
 - ii. Create a new data set – name ComA1_Impu
 - iii. Change imputations to 20
 - b. Method tab
 - i. Custom – select fully conditional specification (set to 50 iterations)
 - ii. Model type – change to PMM – chose from 5 closest (as is default)
 - c. Constraints tab
 - i. Scan data
 - ii. Under define constraints – set all Endpoint variables as impute only.
 1. Instead of clicking use tab and I, plus directional keys to change this.
 - d. Output tab
 - i. Tick imputation model, descriptive statistics and create iteration history – name ComA1_iter
 - e. Double check – click ok
3. Save the imputed and iterations files.

Sequence for multiple imputation.

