BLNFS, BLDGendermale1female2, BLBMI, BLNEnergykcal, BLNCarbohydrateg, BLNProteing, BLNFatg, BLN Sugarsg, BLNFreeSugarsg, BLNFibreg, BLNSaturatedFatg, BLSSodiumNamg, BLWeightkg, BLWaistcircumferencecm, BLLTEShealthscore, BLFCQ1Health, BLFCQ2Mood, BLFCQ3Convenience, BLFCQ4SensoryAppeal, BLFCQ5NaturalContent, BLFC1Q6Price, BLFCQ7WeightControl, BLFCQ8Familiarity, BLFCQ19EthicalConcern, BLSQPC1Personalimpact, BLSQPC2Personalmanagement, BLSQPC3Nonchalance, BLSQPC4Negativity, BLSQPC5Perceivedunderstanding, BLSQPC6PerceivedNonautonomy, BLSF36PCS, BLSF36MCS, BLTSEQ CR, BLTSEQQUE, BLTSEQEE. *Followed by imputation only variables

Get pooled descriptives for analysis / comparison to my values.

1. Data - Split file
 - a. Click split file in ComA1_imp
 - b. Click compare groups
 - c. By imputation number_variable
 - d. Ok
2. Analyze – Descriptive statistics
 - a. Descriptives
 - b. Input all BL and EP variables apart from BL OG FS%.
 - c. Scroll to bottom of output table for pooled means – SD will be calculated from average of 20 imputations at a later date and are not shown here.

BLINDING

The main researcher had no knowledge of allocated groups of participants and was blinded during all data handling and imputation.

DATA ANALYSIS

Outcomes

Primary outcomes were % TEI from free sugars (%FS), and adherence to the recommendations at 12 weeks. Secondary outcomes were dietary profiles (daily energy intake, dietary composition, food consumption), anthropometry, sweet food perceptions and preferences, sweet food choice, attitudes to sweet foods, attitudes towards eating behaviour, motives for food choice, knowledge and lifestyle variables, quality of life and adverse events at week 12; change between baseline and week 12 in key outcomes (%FS, daily energy intake, sugar-sweetened and sweetener-sweetened food consumption, anthropometry), %FS, adherence, dietary profiles and barriers and facilitators towards intervention adherence and success/failure in achieving the recommendations (subset only) at weeks 1, 2, 4 and 8. Demographic variables, and sweet taste sensitivity, sweet liker status and PROP (bitter taste) status were also assessed at baseline, to aid in the interpretation of all outcomes, considering associations between these variables and sweet taste perceptions, liking and food intakes (Jayasinghe et al., 2017; Yeomans et al., 2009).

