Primary models will include gender, age, control/intervention group, baseline %FS, baseline body weight (as randomization variables), and baseline variable of interest. In analyses for %FS, sugar-sweetened food intake, LCS-sweetened food intake, body weight and waist circumference, TEI at Week 12 and physical activity at Week 12 will also be included. Secondary models will also include any additional variable that correlates with each outcome when assessed independently. All variables measured will be considered as secondary variables. Effects for all continuous variables will be investigated using linear multiple regression. Effects for adherence will be investigated using logistic regression to predict adherent vs not adherent.

Analyses Two: Quantitative Data

For analyses two, analyses one will be repeated for demographic groups where significant associations for these variables were found in analyses one. Analyses will only be conducted if significant associations are reported. If no significant associations with demographic variables are found, these analyses will not be completed. These analyses are intended to demonstrate differing effects of the intervention/s in different population groups.

Analyses Three: Qualitative Data

Analyses three will investigate the qualitative data collected from a subset of participants using solo interviews. These interviews were scheduled for completion in a sample of 80 participants from different intervention groups and at different time points. These analyses will be undertaken using a thematic framework analysis. First, a random sample of interviews will be analysed inductively using thematic analysis to identify codes. These codes will be used to create a framework and the framework then applied to all interviews.

Framework analysis has been chosen as a suitable analytical method for evaluating the qualitative interview data gathered, due to an interest in individual experiences and seeks to identify the different factors (barriers or facilitators) that contributed to successful or unsuccessful dietary change (Braun & Clark, 2013). The practical methods for conducting framework analysis follow a methodology as outlined below.

Framework analysis (Braun & Clarke, 2006; 2013; Gale et al, 2013).

Phase 1 'Familiarizing yourself: Transcribing data (if necessary), reading and re-reading the data, noting down with your data: initial ideas'.

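### The imputation leaves out age and every other demographic except gender, so the demographic coefficients that decide whether Analyses Two runs are pulled towards zero by about 11–20% at 20% missing

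*SAP*

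**What the plan says.** Three SAP statements bear on which variables predict the missing week-12 values.

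- **Step-by-step rule** (Instructions for multiple imputation in SPSS): the model "is all endpoint and corresponding baseline variables, therefore excluding demographics. But including gender".
- **Printed list** (Sequence for multiple imputation): it begins "BLNFS, BLDGendermale1female2, BLBMI, BLNEnergykcal, BLNCarbohydrateg, BLNProteing, BLNFatg" and names 35 baseline variables covering diet, anthropometry and questionnaires. Gender is the only demographic. A note says that the imputation-only variables follow, so the 35 read as the full predictor set for the main run.
- **General statement** (All data – Multiple imputation): "All baseline variables were used as predictors, all endpoint variables used as imputations only due to the monotonic pattern".

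Under Analyses One, every primary model contains age, gender, group, baseline %FS, baseline body weight and the outcome's own baseline. Secondary models add any measured variable that correlates with the outcome. Analyses Two repeats this in demographic groups, but "Analyses will only be conducted if significant associations are reported".

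On incomplete variables the SAP says: "Where variables presented as having missing data, they were set as 'impute only' to ensure all predictor variables were not based on imputed data". On the other runs it says: "The same multiple imputation model was run for the initial analyses, adherence and variables completed by only lab participants". Protocol section 7.3 adds that "Participants who are tested 'at-home' will not undertake the sweet taste perception and preference tests"; they also skip the sweet food choice test. The SAP describes sweetened-food counts with a baseline score, but no count, taste-test or sweet-food-choice baseline is in the printed list. The FCQ entries there are the food choice questionnaire, a different measure.

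**The concern.** An imputation model should contain every variable in the analysis model. If age is left out, the imputed week-12 values relate to age only through whatever the other predictors happen to carry. Pooling them with the observed values pulls the age coefficient towards zero.

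Here that coefficient does more than adjust. Significance of a demographic in Analyses One opens Analyses Two, so attenuation makes a pre-specified subgroup analysis less likely to run. The correlation screen for secondary models would use the same weakened associations. The SAP's reason for limiting predictors is to avoid imputing from imputed values. That gives no reason to drop age, which the eligibility range of 18–65 years implies is known for everyone.

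A related question is whether each outcome's own baseline was a predictor. Where it was not, the imputed values are noisier than they need be, and the treatment contrast for that outcome loses precision.

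**Working it through.** The SAP gives no figure for either effect, so there is none to reproduce.

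**Inputs from the documents.** N = 242; 20 imputations; predictive mean matching from 5 donors. The share of week-12 values missing, *f*, is about 20%: the SAP says that 20 imputations matches the percentage attrition, and protocol section 4.2 allows 20%. As a rough check, 242 participants × 24 scheduled diary days = 5808. The SAP reports 5120 daily totals, or 88.2%, so 11.8% of days are missing over the whole trial. That is compatible with about 20% at the endpoint but does not prove it.

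**Assumed, because the documents do not give them.** Values missing completely at random; *f* from 10% to 30%; R² (the share of the omitted demographic explained by the included predictors, beyond the covariates already in the analysis model) from 0 to 0.4; baseline–endpoint correlation from 0.3 to 0.8.

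**1. Coefficient of an omitted demographic.** The observed share (1 − *f*) carries the true slope β. The imputed share *f* carries only β × R². Hence

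expected coefficient ≈ (1 − *f*)β + *f*βR² = β[1 − *f*(1 − R²)].

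The simulation used four arms, 33 other baseline predictors, pooling by Rubin's rules and 400 runs per scenario, with trial arm kept in the imputation so that only the omission of age varies.

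| *f* | R² | Formula | Simulated | Shrinkage (simulated) |
|---|---|---|---|---|
| 20% | 0 | 1 − 0.2 × 1 = 0.80 | 0.79–0.80 | about 20% |
| 20% | 0.2 | 1 − 0.2 × 0.8 = 0.84 | 0.84 | about 16% |
| 20% | 0.4 | 1 − 0.2 × 0.6 = 0.88 | 0.89 | about 11% |
| 10% | 0 | 1 − 0.1 × 1 = 0.90 | 0.90 | 10% |
| 30% | 0 | 1 − 0.3 × 1 = 0.70 | 0.69 | 31% |

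With age, arm and own baseline all included at *f* = 20%, the age coefficient is 0.98–1.00 of truth. Omitting age alone leaves the treatment effect at 0.95–0.99 of truth, against 0.96–0.99 with everything included.

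**2. What this does to the trigger.** In a separate illustration, the outcome was 0.5 × baseline + 0.2 × age + arm effects + noise with SD 0.85, with 20% missing and one of ten predictors correlated 0.3 with age. The pooled age slope was 0.162 without age in the imputation (0.162/0.20 = 81%) and 0.196 with it. Power to find it significant was 78% and 88% respectively. The size of slope is assumed.

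**3. Own baseline, if it was left out (*f* = 20%).** Pooled standard error of a treatment contrast:

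| Assumed correlation | Baseline in | Baseline out | Increase |
|---|---|---|---|
| 0.3 | 0.1899 | 0.1937 | 2% |
| 0.5 | 0.1720 | 0.1859 | 8% |
| 0.7 | 0.1395 | 0.1721 | 23% |
| 0.8 | 0.1139 | 0.1626 | 43% |

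The own-baseline coefficient also shrinks by about 20%.

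**The case against.** **Age may have been in after all.** The general statement says that all baseline variables were predictors, and age is a baseline variable. But the step-by-step rule excludes demographics in terms, and the printed list, given so that the run can be reproduced, has no age. A general sentence does not override both. If age was in fact used, the rule and list are wrong and must be corrected.

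**The imputed values are not unrelated to age.** They are conditioned on 35 baselines, including BMI, waist, physical health score and diet. This stands: a flat 20% is the figure for a demographic that those predictors do not explain at all, which is why a range is given. Gender is in the model and does not shrink for this reason.

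**The primary comparison is hardly touched.** This also stands for the omission of age taken alone.

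**A reader might infer that the rules leave out the own baselines of the food counts and lab-only tests.** The documents do not show this. The rule itself asks for corresponding baselines. No list is printed for the lab run, and describing it as the same model may refer to settings. If that run held lab participants only, their baseline scores could be complete and the impute-only rule would not exclude them. The imputation-only variables are not printed, so it is not even clear that the counts were imputed. Baseline energy, sugars and carbohydrate could also stand in for part of a missing count baseline, which would reduce the loss. What remains is a contradiction between the rule, the printed list and the two sentences on the same model and on incomplete variables.

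**Conclusion.** The point on age and the other non-gender demographics holds. The instructions and the printed list exclude them, the analysis models and the Analyses Two trigger use them, and a third SAP statement conflicts with both. At about 20% missing, the coefficient of such a demographic is understated by about 11–20%, for R² between 0.4 and 0; with R² of 0 it is 10% at 10% missing and 31% at 30% missing. These figures assume values missing completely at random, and the R² values are not in the documents. The direction is clear: the trigger is biased towards not opening.

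It would go too far to say that all demographic effects shrink by 20%, or that omitting age biases the comparison between arms. Trial arm is also absent from the printed list; that is a separate matter, and the statement about the treatment effect here isolates age.

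The own-baseline point is conditional. If those baselines were left out, the precision loss runs from 2% to 43% of the standard error, depending on a correlation that the documents do not give. Whether they were left out cannot be settled from the text.

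**What to change.** 1. Add age, and every other demographic used in Analyses One or Two that is complete at baseline, as imputation predictors, and re-run.
2. Correct the general statement, the step-by-step rule and the printed sequence so that they name the same predictor set.
3. Print the predictor and imputation-only lists for the main, adherence and lab-only runs, and say whether the food counts were imputed.
4. If the count baselines were left out, add them as predictors of their endpoints.
5. If the lab-only baselines were left out, impute and analyse those outcomes among participants tested in the lab at baseline, with the baseline score as a predictor. Define this group by baseline location: baseline testing precedes randomisation, whereas protocol section 7.3 keeps the same location at trial end only where possible.

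The cost is one re-run with a few more predictors and a text correction; no new data are needed. The downside of step 5 is that the lab-only results then apply only to lab-tested participants.

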Three distinct analyses were pre-specified in advance: 1) Analyses of the population as a whole to investigate the effects of the three different types of dietary recommendation versus control; 2) Analyses of the effects of the dietary recommendations in different population subgroups, and 3) Investigation of the barriers and facilitators to success.

Data presentation

Data will be presented as mean \pm standard deviation in all cases, unless stated. Values will be considered significant at the $p<0.05$ level. Before completing analyses, data will be checked for normality. The data set is large, $N=242$, thus a normal distribution will be assumed. Where assumptions of homogeneity of variance are violated (Levene's test $p<0.05$), statistics will be taken from analyses conducted assuming non-equal variances. Bonferroni corrections for multiple testing will be applied to data where tests were not pre-specified in the study protocol. Where multiple regression analyses are used, all variables will be checked for multicollinearity using correlation cut-offs of <0.7 . Pearson correlation values will be used for all continuous variables, and Spearman correlations for categorical variables.

Participant characteristics

Details of study completion will be provided and a CONSORT diagram created detailing number randomized to each group, number completing the study in each group, drop out and number included in all analyses.

Characteristics will be given for the whole sample and for each trial group.

Analyses One: Quantitative Data

For analyses one, multiple regression analyses will be used. Analyses will be conducted for both primary outcomes, for key secondary outcomes - daily energy intake, sugar-sweetened food intake, LCS-sweetened food intake, body weight, waist circumference, and adverse events; and change (baseline - week 12) data for these outcomes; and for other secondary outcomes (dietary

composition, sweet food perceptions and preferences, sweet food choice, attitudes to sweet foods, attitudes towards eating behaviour, motives for food choice, knowledge and lifestyle variables, quality of life) if differences are found in the sample as a whole from baseline to week 12. This will reduce the number of exploratory tests undertaken. Differences from baseline to week 12 will be investigated by paired t-tests. Primary outcomes and outcomes associated with dietary composition will also be investigated in the same manner at weeks 1, 2, 4 and 8.

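### The SAP's unequal-variance rule names no procedure and is not tied to the linear regressions that compare the arms on continuous outcomes

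*SAP*

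**What the plan says.** **Unequal variances.** The SAP, Data presentation, sets a Levene's test at p<0.05 as the trigger: "Where assumptions of homogeneity of variance are violated", "statistics will be taken from analyses conducted assuming non-equal variances". No procedure is named, and it is not said whether the test is run on raw outcomes or on model residuals. In the same paragraph normality is taken from the sample size of 242: "thus a normal distribution will be assumed". Section 8 of the protocol says only that parametric assumptions will be checked.

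**Tests to which the rule might apply.** The only t-tests in the SAP are paired, in the sample as a whole: "Differences from baseline to week 12 will be investigated by paired t-tests". The comparison of arms is made otherwise. SAP, Analyses One: "For analyses one, multiple regression analyses will be used", then "Effects for all continuous variables will be investigated using linear multiple regression" and "Effects for adherence will be investigated using logistic regression to predict adherent vs not adherent". Protocol section 8.1 also specifies multiple regression. The arm term is listed among the model variables, but its coding (three dummies, or one control-versus-any-advice indicator) is not given.

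**Count data.** SAP, Sweetener and sweet food counts: "Foods that contained sweeteners, were high, medium or low in sugar were separated into counts for each diet diary". No count model is named anywhere.

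**The concern.** A paired t-test works on a single set of differences, so it has no equal-variance and unequal-variance versions. The rule therefore has no use there. It would be needed in the linear regressions, and for these the SAP does not say what assuming unequal variances means. Without further instruction, an analyst would report the ordinary least-squares standard errors, which use one residual variance averaged over all arms.

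Equal allocation protects a two-group comparison with pooled variance. It does not protect a two-arm contrast when the variance is pooled over four arms, because two of those arms contribute to the standard error but not to the contrast.

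Unequal spread is plausible here, though not established. %FS cannot fall below zero, participants enter above 5% of energy, and three arms are advised to go below 5% while control receives no advice. Only the NFS arm receives the pages on sweeteners and low-sugar versions, so its counts of sweetener-containing foods may shift, and the variance of a count usually rises with its mean. A sample of 242 helps the estimates towards normality but does not correct a wrong standard error.

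At stake is the precision claimed for the three advice-versus-control effects, including those on %FS. A test-then-switch rule with no named destination also leaves the choice of analysis open until the data have been seen.

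**Working it through.** The plan states no figure for unequal variances or interval coverage, so there is none to reproduce.

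**Inputs.** Four arms (protocol section 3); 60 per arm and 20% attrition (section 4.2), so 60 × 0.8 = 48 completers per arm; a difference of 2 points and a standardised difference of 0.8 (section 4.2), so an implied SD of 2/0.8 = 2.5. The documents give no SD by arm. The arm SDs below are assumptions set around 2.5; only their ratios affect the result.

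**Formula.** With equal arms of size n and three arm dummies, the pooled variance is the mean of the four arm variances, s̄². For arm k against control (0):

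- model variance = 2s̄²/n
- true variance = (s₀² + s_k²)/n
- ratio r of model SE to true SE = √[2s̄² / (s₀² + s_k²)]; n cancels
- coverage of a nominal 95% interval ≈ 2Φ(1.97 r) − 1

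**Example 1, control 1.5 times the rest (3.75 against 2.5).** s̄² = (14.06 + 3 × 6.25)/4 = 8.20. r = √(16.41/20.31) = 0.90. Coverage is 92.4%: too narrow.

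**Example 2, all advice arms 1.5 times control.** s̄² = (6.25 + 3 × 14.06)/4 = 12.11. r = √(24.22/20.31) = 1.09. Coverage is 96.9%: too wide.

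**Example 3, one advice arm 1.5 times the rest.** s̄² = 8.20 again. For that arm's contrast r = 0.90, as in example 1. For the other two, r = √(16.41/12.50) = 1.15 and coverage is 97.6%. The error then runs both ways among the advice-versus-control contrasts themselves.

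The formula was checked by simulation: 10,000 runs, four arms of 48, one baseline covariate, ordinary least squares (OLS) against HC3.

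| Assumed SD: control; advice arms | r | Coverage, formula | OLS, simulated | HC3, simulated |
|---|---|---|---|---|
| 2.5; all 2.5 | 1.00 | 95% | 95.1–95.4% | 95.1–95.4% |
| 3.75; all 2.5 | 0.90 | 92.4% | 92.0–92.7% | 95.0–95.4% |
| 2.5; all 3.75 | 1.09 | 96.9% | 96.7–96.9% | 95.1–95.2% |
| 2.5; one at 3.75, two at 2.5 | 0.90 (that arm), 1.15 (others) | 92.4%, 97.6% | 92.3%, 97.6–97.7% | 95.3–95.6% |
| 5; all 2.5 | 0.84 | 90.1% | 90.0–90.6% | 95.2–95.7% |
| 2.5; all 5 | 1.14 | 97.6% | 97.2–97.6% | 95.0–95.4% |

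A milder ratio of 1.25 (control 3.125, others 2.5) gives r = 0.94 and 93.7% by the formula.

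**If the arm term is one control-versus-any-advice indicator (1:3).** Model variance is s̄² × 4/(3n). Control at 3.75: r = √(10.94/16.15) = 0.82, coverage 89.5%. All advice arms at 3.75: r = √(16.15/10.94) = 1.22, coverage 98.3%. The problem exists under either coding and is larger under this one.

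**Cost of HC3 when variances are equal.** Mean interval width was 2.039 against 2.015 for OLS, about 1.2% wider (2.039/2.015 = 1.012).

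The simulation used complete data; it did not include multiple imputation or the full covariate list.

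**The case against.** The strongest reply is that the SAP does provide for unequal variances, in general words that do not exclude robust or weighted regression, and that only a clarification is missing. Part of this stands. A reader might infer that the rule is a t-test remedy misapplied to regression. The wording resembles that, but the SAP names no procedure, so the supportable statement is that the remedy is unspecified and not connected to the model. That is still worth fixing, because a preliminary test leading to an unnamed analysis is weaker than a standard error that is valid in either case.

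Other stronger readings are also unsupported:

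- **That every between-arm test is affected.** Adherence, one of two primary outcomes, uses logistic regression and has no pooled residual variance. The model for adverse events is not specified.
- **That the intervals are in fact wrong.** This depends on arm SDs that the documents do not give. The SAP also states a p<0.05 criterion, not an interval level; 95% is used here as its counterpart.
- **That false positives against control are inflated.** Assumed SDs of 5 for control and 3 for each advice arm give s̄² = (25 + 27)/4 = 13, r = √(26/34) = 0.874 and a type I error of 8.7%. But that needs equal means with unequal spread. If spread changes because advice lowers intake, it does not arise when advice has no effect. Coverage is the safer measure.
- **That the ranking of advice arms is distorted.** Analyses One is defined as each type of advice versus control; advice-versus-advice contrasts are not specified.
- **That the food counts require a negative binomial model.** The SAP does not expressly say that these counts are the sugar-sweetened and LCS-sweetened intake outcomes. It also analyses change from baseline, which can be negative and cannot be fitted that way.

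**Conclusion.** The point holds for the linear models, including the one for %FS. The SAP's only unequal-variance provision is a Levene-triggered switch to unspecified analyses, and nothing ties it to the regressions that compare the arms. If residual spread differs by arm, the pooled standard error is wrong in spite of equal allocation.

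The size is modest and conditional. With arm dummies and assumed SD ratios up to 1.5, coverage of a nominal 95% interval for advice versus control is about 92% to 98%; at a ratio of 2 the too-narrow intervals cover about 90%. The direction depends on which arm is more variable. These figures assume equal arms and complete data. Whether the variances do differ cannot be known from the documents. The change is worth making because HC3 kept coverage at about 95% in every scenario simulated, with almost no cost when variances were equal.

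**What to change.** Replace the Levene-triggered sentence in SAP, Data presentation, with: *All linear models report heteroscedasticity-consistent (HC3) standard errors, pooled over the 20 imputations by Rubin's rules.* Apply it also to the linear models for the food-count outcomes and for the change scores. State the coding of the arm term in the same place, so that it is clear which contrasts the standard errors belong to.

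A negative binomial model for the week-12 food counts is an optional addition, not part of this change.

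Cost: one sentence of SAP wording, intervals slightly wider when variances are truly equal (about 1% in the simulation), and some manual pooling. The SAP already provides for Rubin's rules where the software does not pool automatically.
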